The actions of GH in adipose tissue are central to its effects to reduce adipose tissue mass. GH may have effects both on adipocytes as well as inflammatory cells in adipose tissue. Thus GH effects in adipose tissue may importantly relate to adipose tissue and thus circulating inflammation in disorders of GH secretion. In our ongoing study examining the effects of GH excess on adipose tissue changes in acromegaly, our preliminary identified that GH produces a unique adipocyte-immune cell phenotype that contributes to circulating inflammation and insulin resistance and may alter adipose tissue energy metabolism. Our hypothesis stems from our identification in preliminary work of a novel and unexpected GH-induced dissociation of inflammatory & immune phenotypes. Specifically, we found a pro-inflammatory pattern of adipocyte activation yet suppression of macrophage inflammation that reverses with acromegaly treatment. GH-induced increased lipolysis may initiate these effects. GH increases HSL, reduces LPL activity and activates the α -adrenergic 3 receptor (18, 39-44). GH also inhibits lipogenesis and reduces AT mass (41, 45). In other models, disordered lipid metabolism promotes lipolysis and FFA release leading to pro-inflammatory cytokine release. This inflammatory response then promotes insulin resistance in adipose tissue (46-55). Thus, cytokines released by inflamed adipose tissue may play a role in GH induced insulin resistance. The effect of GH excess on AT inflammation had not been examined before our study. By contrast, in other models, activation of inflammatory (adipocyte cytokine) and immune (macrophage) components of AT parallel each other. Our findings are supported by recent in vitro data that GH induces pro-inflammatory cytokines in pre-adipocytes yet suppresses inflammatory cytokines in macrophages (56). This study examined isolated cells (56, 57), ours provides evidence of this effect in vivo. In this study, we will test the effect of restoration of GH secretion through administration of GHRH analogue therapy on AT inflammation in HIVLD groups. In patients with GHD with central obesity, as shown in a cross-sectional study, SAT phenotype may be similar to that of general obesity, namely increased adipocyte size and expression of pro-inflammatory factors and macrophage infiltration (58).

Effects of GH therapy are unknown, but it may reduce both adipocyte and macrophage inflammation.

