The primary hypothesis to be tested is that therapy with the GHRH analog tesamorelin, which augments GH secretion), will reduce hepatic lipid and visceral adipose tissue mass in patients with HIV lipodystrophy and central adiposity. The second hypothesis to be tested is the tesamorelin therapy will reduce adipose tissue inflammation and circulating pro-inflammatory markers on macrophages in these patients.

STUDY DESIGN

The CORE study is an open-label, single arm prospective study of tesamorelin therapy of patients with HIV lipodystrophy.

Enrolled subjects will have a screening visit and 6 visits - a baseline visit before starting tesamorelin, a visit at 1 month, 3 months, 6 months, 9 months and at 1 year of tesamorelin (GHRH analogue) therapy. Blood sampling for safety labs and clinical examinations will be performed at each visit. At the baseline, 6 month and 1 year visits subjects will also undergo body composition testing by total body MRI/MRS, adipose tissue biopsy, indirect calorimetry, FSIGT and additional blood sampling. Tesamorelin is being used in this study as per its FDA approved indication and dosing for treatment of HIV lipodystrophy with central adiposity. Tesamorelin, 2 mg, will be taken daily by patients by subcutaneous self-injection

Subject Inclusion Criteria:

- HIV-infected subjects with HIV lipodystrophy (HIVLD) and abdominal fat accumulation.
- Males and females
- Ages 18-65 years
- Waist Circumference (WC): 102 cm for men, 88 cm for women (ethnicities except East/South Asians) 90 cm for men, 80 cm for women (East/South Asians)
- CD4 count >100 cells/mm³.
- HIV RNA load < 400 copies/mL

- Fasting glucose <150 mg/dL
 - Patients with mild diabetes (HbA1c<7%) that is well controlled with diet and/or oral diabetic agents besides TZDs are eligible.
- Stable antiretroviral therapy for 8 weeks (any regimen).

Exclusion criteria:

- Diabetes mellitus that is not well controlled
- History of malignancy

Study procedures

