Total body MRI: Quantification of total and regional body composition by whole body multi-slice MRI, liver fat by Modified DIXON method (35, 79), and ¹H-MRS (magnetic resonance spectroscopy) assessment of intra-hepatic lipid (IHL) and IMCL of the anterior tibialis muscle will be performed at the Columbia Hatch MR Research Center as previously described (80, 81). Analyses will be done in the NY Obesity Research and Nutrition Center Image Analysis Lab on the CUMC campus and under the direction of [name] (80, 81). The analysis will include measurement of inter-muscular AT (IMAT)(AT between muscle groups and beneath the fascia (82, 83), which is distinct from intra-myocellular lipid (IMCL)(lipid in myocytes). MRIs will be analyzed by the same experienced reader blinded to study conditions using SliceOmatic software (TomoVision) (82, 84). Liver fat will also be determined by Modified DIXON method performed during the total body MRI sequences. It has advantages of not requiring ROI selection during acquisition and measures fat for the entire liver. DIXON is validated against MRS (35, 79).

Adipose tissue biopsy: After a 12-hour fast, subjects will undergo abdominal subcutaneous AT biopsy by the PI at the umbilicus level. Alternating sides of the abdomen will be samples on serial biopsies. After local anesthesia, 2-4g of AT will be using aspirated using a 15g needle. Pieces will be immediately frozen in liquid nitrogen & stored at -80°C, others are fixed for immunohistochemistry.

Indirect Calorimetry (TrueOne2400, ParvoMedics) will measure resting energy expenditure (REE) after an overnight fast (12hr.) and 30 min. of rest with subjects still, awake and supine in a thermoneutral environment. REE will be determined from the last 20 minutes of 30 minutes of gas exchange results (85). The cart is calibrated prior to each test (86).

Insulin-modified frequently sampled intravenous glucose tolerance test (FSIGT) with reduced sample number (n=12)(87) will be performed to assess insulin sensitivity. In this protocol, a 300 mg/kg bolus of glucose will be administered after an overnight fast followed by an infusion of 0.03 units/kg of insulin 20 minutes later. In the reduced sample model, 12 blood samples (insulin and glucose) will be drawn at times 0, 2, 4, 8, 19, 22, 30, 40, 50, 70, 90 and 180 minutes (22). The data will be analyzed by Bergman Minimal Model to calculate our outcome measures, insulin

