Immuno-histochemical analysis: Macrophage antigen, CD68, expressing cells fraction/sample will be calculated to determine macrophage content (94). Adipocyte size will be measured (Image-Pro Plus, Media Cybernetics, Bethesda, MD) (95) and size distribution will be quantified (96). Adipocyte count, counts of crown-like structure and other immune (T, NK) cells and fibrosis analysis will be conducted (97). Sample processing and analyses will be uniform and paired samples will be directly compared. Quantitative RT PCR will be performed on total RNA extracted from frozen AT as described (94). Relative expression values will be determined for: adipocyte-specific genes adiponectin (ADIPOQ) and leptin (LEP), proinflammatory genes (TNF,

IL6), genes of macrophage activation markers (CD11c, CD68, MCP-1, IL1- Genes associated with AT “browning” (UCP-1, DIO2, CIDEA, PGC-1, PRDM-16), and lipid metabolism, (CIDEA, PLPLA3, SCD, PIK3R1, TCF7L2). We will use control genes to normalize data (94). Samples are analyzed in labs of [name] and NYONRC AT core.

HORMONE ASSAYS: Hormones and other markers will be measured with the following assays: IGF-1 (WHO 02/254) & GH (WHO 98/574, 22kDa GH specific antibody), IDS-iSYS chemiluminescence assay; IGF-1 & GH (WHO 98/574, 22kDa & 20kDa antibody), Insulin, IGFBP-3, hsCRP - chemiluminescent immunometric (Immulite, Siemens); HbA1C, glucose, lipids (Cobas Integra, Roche); Adiponectin (total & HMW)- ELISA (Millipore); Leptin- RIA (Millipore); FFA - enzymatic colorimetric (WAKO); IL-6 & TNF -ultrasensitive ELISA R & D.

STATISTICAL PROCEDURES

The primary outcome to be examined will be change in hepatic lipid content and the secondary outcome will be change in VAT mass with tesamorelin therapy. Additional outcomes examined will be changes in relative gene expression of adipose tissue genes, change in Si, REE and changes in other hormones and markers with tesamorelin therapy.

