The general analytic approach will be to compare baseline to post-therapy parameters in each subject by paired t-test. Repeated measures ANOVA will test adipose tissue mass change over time. Correlations between variables will be tested by Pearson’s correlation. Non-normally distributed data will be log-transformed or nonparametrics used. Multiple comparisons corrections and post-hoc tests will be used. Macrophage content (% CD68 positive cell per sample) and average adipocyte cross-sectional area will be compared in HIV lipodystrophy patients adipose tissue before vs. after tesamorelin therapy by paired t-test. Adipocyte area and macrophage content will be correlated with BMI and fat mass. Correlations between gene expression data and body mass or AT mass will be compared by a nonparametric approach. Ratios of macrophage content or relative gene expression per kg AT will be compared in patients before & after treatment by appropriate t-tests. For analysis of the blood samples differences between baseline and final study visit for each marker will be compared by paired t-test. Patterns and time course of change in serum and adipose tissue inflammation will be descriptively compared. Matching serum/gene expression marker changes will be correlated.

Sample Size is based on the number of subjects needed to detect a significant decrease in hepatic lipid with tesamorelin therapy. Preliminary data from our acromegaly treatment study were used for this estimation. Sample size of 24 pairs has 88% power to detect a hepatic lipid change of 2% with a SD of 3% at $\alpha = .05$ and 12 pairs of each gender has 80% power to detect this hepatic lipid change within gender group with a within-gender SD of 2% at $\alpha = .05$ using a two-sided paired t-test.

REFERENCES

3. Stanley TL and Grinspoon SK (2012) Body composition and metabolic changes in HIV-infected patients. *The Journal of infectious diseases* 205 Suppl 3: S383-90. 3349298.

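### The before/after t-tests of macrophage content and gene expression per kg of adipose tissue mix fat loss with inflammation change; this additional comparison is wrong as written, while the undivided paired tests are unaffected

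*Combined protocol and SAP*

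**What the plan says.** Under Statistical Procedures, the combined protocol and SAP states: "Ratios of macrophage content or relative gene expression per kg AT will be compared in patients before & after treatment by appropriate t-tests". It gives no reason for dividing by AT mass and does not name the depot.

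The numerators are defined in the paragraph on immunohistochemistry and PCR under Adipose Tissue Analyses. For macrophages: "Macrophage antigen, CD68, expressing cells fraction/sample will be calculated to determine macrophage content". For expression, relative values are determined and "We will use control genes to normalize data". The tissue is subcutaneous: "subjects will undergo abdominal subcutaneous AT biopsy by the PI at the umbilicus level" (Adipose tissue biopsy, under Study procedures).

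The expected direction of the denominator appears in two places. The primary hypothesis (Research Aims & Abstracts) is that tesamorelin "will reduce hepatic lipid and visceral adipose tissue mass in patients with HIV lipodystrophy and central adiposity". The Background says: "The actions of GH in adipose tissue are central to its effects to reduce adipose tissue mass". No size is given for either.

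The second hypothesis is that "tesamorelin therapy will reduce adipose tissue inflammation and circulating pro-inflammatory markers on macrophages in these patients".

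Statistical Procedures also plans a paired t-test of the percentage of CD68-positive cells before and after therapy, and lists change in relative expression, undivided, among the additional outcomes. Hepatic lipid is the primary outcome and VAT mass the secondary.

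**The concern.** Dividing by mass makes sense when the numerator is a total that grows with the amount of tissue. Here neither numerator does: a cell fraction and a control-gene-normalised expression value describe the sample whatever the patient's fat mass. Dividing them by kilograms of AT adds a second quantity that treatment is itself expected to change, so the t-test responds to fat loss as well as to inflammation.

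For inflammatory markers the artefact works against the second hypothesis, and it grows with the drug's effect on fat. For genes hoped to rise it works the other way. The ratio sentence covers relative expression in general, the gene list includes browning genes, and the Background suggests that browning may accompany therapy. For those genes fat loss alone would produce a rise in the hoped-for direction, so the ratio cannot be defended as merely conservative.

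The depot matters too. The biopsy is subcutaneous and the hypothesised loss is visceral. If the kilograms are visceral or total AT, a subcutaneous measure is divided wholly or partly by the mass of tissue that was not sampled. Because the depot is not named, the choice that sets the size of the artefact is left open.

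**Working it through.** **Inputs from the document.** 24 pairs; two-sided paired t-test at alpha .05. Both are stated for the hepatic lipid sample size. The plan gives no power, effect size or SD for the ratio.

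**Inputs assumed.** Proportional AT loss L of 2, 5, 10 or 15%; SD of the within-patient log change of 0.3, 0.4 or 0.5; all 24 pairs available.

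**Check of the method on the plan's own figure.** For a paired t-test the noncentrality is (change/SD) × √n. With 2/3 × √24 = 3.27 on 23 df, power is 87.8%, which reproduces the stated 88% for hepatic lipid.

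**Step 1: effect on the ratio.** If the marker falls by a proportion F and AT mass by L,

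ratio change = (1 − F)/(1 − L) − 1.

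With F = 0 this is 1/(1 − L) − 1. For example, L = 0.10 gives 1/0.90 − 1 = +11.1%.

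**Step 2: chance of a significant spurious rise.** On the log scale the shift is −ln(1 − L), and the noncentrality is that shift divided by the SD, times √24. For L = 0.10 and SD 0.3: 0.1054/0.3 × 4.899 = 1.72, giving 38%. The nominal rate in this direction is 2.5%.

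| AT loss | Ratio change, marker unchanged | SD 0.3 | SD 0.4 | SD 0.5 |
|---|---|---|---|---|
| 2% | +2.0% | 5% | 4% | 4% |
| 5% | +5.3% | 12% | 9% | 7% |
| 10% | +11.1% | 38% | 24% | 17% |
| 15% | +17.6% | 72% | 48% | 33% |

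**Step 3: what happens to a true fall.** From the formula in step 1:

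- F = L: no change. A 15% fall with 15% AT loss gives 0.85/0.85 − 1 = 0.
- F < L: an apparent rise. A 10% fall with 15% AT loss gives 0.90/0.85 − 1 = +5.9%.
- F > L: a smaller fall. A 20% fall with 10% AT loss gives 0.80/0.90 − 1 = −11.1%.

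**Step 4: comparison with the undivided marker.** This is a simulation of 40,000 runs with n = 24, SD of log marker change 0.25, SD of log AT change 0.05 and the two changes independent (all assumed except n).

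| AT loss | Marker | Result counted | Undivided | Ratio |
|---|---|---|---|---|
| 10% | unchanged | significant rise | 2.6% | 49% |
| 10% | true 15% fall | fall detected | 86% | 18% |
| 10% | true 20% fall | fall detected | 99% | 58% |
| 2% | true 15% fall | fall detected | 86% | 75% |

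**The case against.** The strongest reply is that the plan does not depend on the ratio. The percentage of CD68-positive cells has its own paired t-test, change in relative expression is a listed outcome without division, and correlations of macrophage content with fat mass and of gene expression with AT mass are already planned. The ratio is neither the primary nor the secondary outcome and does not bear on the sample size. All of this stands. A reader might infer that the plan as a whole hides a true fall in inflammation, or that the test of the second hypothesis is biased throughout. The documents do not support either reading: the direct tests are unaffected, and nothing says the ratio decides the hypothesis.

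The second reply concerns size. Only visceral loss is hypothesised. If the kilograms are total or subcutaneous AT and that mass changes little, the artefact is small: 4–5% against 2.5% for a 2% loss. This also stands, and it is why the large figures must be read as conditional on a 10 or 15% fall in whichever depot is used.

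Neither reply rescues the ratio test. Two analyses of the same samples can disagree purely because fat fell, and the plan does not say which one settles the question. That is a problem of interpretation, not an internal contradiction in the plan, but it is avoidable.

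**Conclusion.** Wrong as written, for one additional, non-primary analysis; moderate severity. That the ratio rises with AT loss when the marker is unchanged is an algebraic identity and needs no assumption. How often this produces a significant false result does rest on assumptions. Over AT losses of 2 to 15% and SDs of 0.3 to 0.5, the probability runs from about 4% to 72%, against a nominal 2.5%. The documents give neither the loss, nor the SD, nor the depot, so no single value in that range can be picked out.

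Complete masking of a true fall is not the general case. It needs a proportional fall no larger than the AT loss; larger falls are shrunk and harder to detect. The conclusions on hepatic lipid and VAT mass are not touched.

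**What to change.** 1. Delete the sentence planning t-tests of ratios per kg AT.
2. State that the undivided paired changes already planned, in percentage of CD68-positive cells and in relative expression (log scale where needed), decide the adipose-inflammation hypothesis.
3. If the question is whether marker change depends on fat loss, regress log marker change on change in AT mass. Name the depot in advance and label the analysis exploratory, since AT change is itself a result of treatment.

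The cost is wording only. The data and procedures stay the same, a set of tests is removed, and the scientific question about fat loss is kept.

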Patients who are interested in the study will first undergo screening. Screening which consist of a telephone interview to further explain the study and confirm the subjects' interest and eligibility and a review of medical records for the above entry inclusion and exclusion criteria. If needed to obtain information on entry criteria not available from the medical record, subjects will have a brief screening visit in person to obtain additional information. If subjects meet all entry criteria and agree they will be enrolled.

Enrolled subjects will have 6 visits - a baseline visit before starting tesamorelin, a visit at 1 month, 3 months, 6 months, 9 months and at 1 year of tesamorelin (GHRH analogue) therapy. Blood sampling for safety labs and clinical examinations will be performed at each visit. At the baseline, 6 month and 1 year visits subjects will also undergo body composition testing by total body MRI/MRS, adipose tissue biopsy, indirect calorimetry, FSIGT and additional blood sampling.

Study Drug Tesamorelin is being used in this study as per its FDA approved indication and dosing for treatment of HIV lipodystrophy with central adiposity. Tesamorelin, 2 mg, will be taken daily by patients by subcutaneous self-injection at rotating sites on the abdomen. Safety assessments including measurements of fasting blood glucose and liver function tests and clinical examinations for signs and symptoms of GH excess or local injection site reactions will be performed at 1 month and every 3 months of therapy.

At the baseline, 6 month and 1 year visits subjects will undergo body composition testing, adipose tissue biopsy, indirect calorimetry for measurement of REE (resting energy expenditure), FSIGT and fasting blood sampling.

Body composition testing: Anthropometrics and total body MRI and ¹H-MRS after a 12 hour fast.

Anthropometric measurements: Subjects will have measurements of waist circumference with a tape measure and height and body weight will be measured.

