sensitivity index (Si) and disposition index (DI) to estimate B-cell function (87-92). FSIGT is used extensively to assess insulin sensitivity and provides estimates that correlate well with those of the clamp in non-diabetics (87, 91, 93).

Blood Sampling: Fasting serum or plasma samples will also be obtained for IGF-1, GH, leptin, FFA, glucose, TNF, IL-6, hsCrp, adiponectin (high molecular weight & total), leptin and lipid panel.

Peripheral blood mononuclear cell collection: A sample (2 tbsp.) of heparinized blood will be obtained. Peripheral blood mononuclear cells will be isolated by density centrifugation using Ficoll (Life Technologies). Recovery of highly purified monocytes will be performed by flow cytometry with fluorophore conjugated anti-CD14 primary antibody. Cells will be analyzed on a FACSCalibur and analysis performed using CellQuest software (Becton Dickinson). Monocytes will be separated using a FACSaria cell sorter (BD Biosciences). CD14⁺ cells will be centrifuged and immediately frozen for later gene expression analysis. PCR will be performed in batches for gene expression of TNF, IL6, MCP-1, IL1-B, IL-4. A complete blood count will be performed from this sample.

The total amount of blood drawn at baseline, 6 month and 1 year visits will be 4 tablespoons and at the other visits it will be ½ tablespoon.

Blood sampling for safety labs and physical examinations: At each visit, blood will be drawn for liver function tests (AST, ALT), and fasting blood sugar. Subjects will also have a physical examination including measurement of vital signs, temperature and examination for signs and symptoms of GH excess such as edema and local skin reactions.

Adipose Tissue Analyses: Frozen and fixed adipose tissue samples will be later analyzed in batches.

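### Blood markers are tested from baseline to an undefined final study visit, with no rule for patients who stop after 6 months

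*Combined protocol and SAP*

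**What the plan says.** The schedule gives three full blood draws. Study Design lists, for baseline, 6 months and 1 year, "indirect calorimetry, FSIGT and additional blood sampling", and Study procedures repeats this as "REE (resting energy expenditure), FSIGT and fasting blood sampling". The Blood Sampling paragraph names the markers: "Fasting serum or plasma samples will also be obtained for IGF-1, GH, leptin, FFA, glucose, TNF, IL-6, hsCrp, adiponectin", with a lipid panel. The volumes agree with this schedule: "The total amount of blood drawn at baseline, 6 month and 1 year visits will be 4 tablespoons", against half a tablespoon at the other visits. Fasting glucose is the exception, because it is also a safety test: "At each visit, blood will be drawn for liver function tests (AST, ALT), and fasting blood sugar".

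Statistical Procedures then says: "For analysis of the blood samples differences between baseline and final study visit for each marker will be compared by paired t-test". The next sentence covers the time course: "Patterns and time course of change in serum and adipose tissue inflammation will be descriptively compared". A repeated-measures method is named for one other outcome only: "Repeated measures ANOVA will test adipose tissue mass change over time". The general approach in that section is a paired t-test of baseline against post-therapy values, with no visit named. The documents give no dropout rate, no rule for patients who stop early and no missing-data method. Changes in hormones and markers are listed as additional outcomes, after hepatic lipid (primary) and VAT mass (secondary).

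**The concern.** The final study visit can be read in two ways. It may be the scheduled 1-year visit or the last visit that each patient attends. The readings agree for patients who complete the year and differ for everyone else.

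The group affected is wider than it first appears. The 9-month visit has no full marker draw, so a patient who attends at 9 months and then leaves still has only a 6-month marker value (fasting glucose aside). Under the first reading that patient is lost from the test. Under the second, a 6-month change is averaged with other patients' 12-month changes. Because the plan does not choose, the choice could be made after the data are seen.

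The study is open-label and single-arm, with a year of daily self-injection and about 24 patients, so a few early stoppers can move a mean change. The second hypothesis under Research Aims includes circulating pro-inflammatory markers, and the Background puts circulating cytokine and adipokine levels within the study's purpose.

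**Working it through.** **The plan's own figure.** There is no power statement for blood markers, so the hepatic lipid inputs serve as a yardstick: 24 pairs, change 2%, SD 3%, two-sided α = 0.05. The standardised change is 2/3 = 0.667 and the noncentrality is √24 × 0.667 = 3.27 on 23 degrees of freedom. Power is 87.8%, which agrees with the stated 88%.

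**Complete data.** With all three visits present and visit fitted as a category, the model's 1-year mean change equals the mean paired difference. In one simulated data set of 24 patients both were −0.6197. The 6-month value adds nothing to this contrast when nobody drops out.

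**Dropout and precision.** Dropout and correlation are assumed here, because the documents give neither. Let r be the correlation between the 6-month and 1-year changes, n = 24, and n_c the number of completers. In units of the change variance:

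- completers only: variance = 1/n_c
- likelihood model keeping 6-month values: variance = (1 − r²)/n_c + r²/n

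At 20% dropout, n_c = 24 × 0.8 = 19.2.

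- r = 0.5: 0.75/19.2 + 0.25/24 = 0.0495, effective n = 20.2
- r = 0.8: 0.36/19.2 + 0.64/24 = 0.0454, effective n = 22.0

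| Assumed dropout | Completers: n, power | With 6-month values, r = 0.5 to 0.8: effective n, power |
|---|---|---|
| 10% | 22, 84.6% | 22.2 to 23.1, about 85 to 86% |
| 20% | 19, 78.5% | 20.2 to 22.0, about 81 to 85% |
| 30% | 17, 73.3% | 18.2 to 20.8, about 76 to 83% |

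Powers use n rounded to a whole number. The variance formula is a large-sample one that treats dropout as unrelated to response.

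**Dropout and bias.** The simulation had 4,000 runs of 24 patients. Each visit had variance 1 and any two visits correlated 0.5, so a change has SD √(1 + 1 − 2 × 0.5) = 1 and r = 0.5. Mean changes were −0.5 at 6 months and −0.667 at 1 year, where a fall is a good response. The chance of leaving after 6 months was logistic in the 6-month change D6: −1.75 + 1.2 × (D6 + 0.5). Average dropout was 20.0%.

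| Method | Mean estimate | Error against −0.667 | Sampling SD |
|---|---|---|---|
| Completers (final = 1 year) | −0.767 | 0.767/0.667 = 1.15, 15% too large | 0.224 |
| Last attended | −0.556 | 0.556/0.667 = 0.83, 17% too small | 0.213 |
| Likelihood-based | −0.667 | none | 0.229 |

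The two readings err in opposite directions. For last attended, random dropout alone would give 0.8 × 0.667 + 0.2 × 0.5 = 0.634, about 5% too small. The rest comes from the leavers being poor responders.

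The sampling SDs show that at r = 0.5 and n = 24 the model's benefit is the removal of bias; it was no more precise than the completers' mean. Root mean squared error still favours it: completers √(0.224² + 0.100²) = 0.245, last attended √(0.213² + 0.111²) = 0.240, likelihood-based 0.229.

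**The case against.** The best defence is that a paired t-test with a descriptive time course is reasonable for additional outcomes in a 24-patient single-arm study. The schedule ends at 1 year, so the final study visit has a natural meaning that one sentence would settle. Part of this stands. The 1-year reading is the more natural one, and with full attendance the planned test is as good as the model for that contrast. But the 1-year reading still drops early stoppers, and no rule covers them.

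It is also fair that repeated measures ANOVA, named for adipose tissue mass, would not solve this. In its classical form it too drops patients with a missing visit. The remedy has to be likelihood-based.

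Three stronger readings are tempting, and the documents do not support them.

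- A reader might infer that a third of the marker data is thrown away. One of three full draws is outside the formal test, but a descriptive comparison over time is planned, the share is wrong for fasting glucose, and with complete data the 1-year contrast loses no information.
- A reader might infer that using both post-baseline visits would sharpen the planned test. The gain belongs to a different target, the average of the 6-month and 1-year changes. Its variance relative to the 1-year change is (1 + r)/2, which is 0.75 at r = 0.5 and 0.90 at r = 0.8. If the 6-month effect were 70% of the 1-year effect, the average would be 0.85 of it, and 0.85/√0.75 = 0.98 at r = 0.5 or 0.85/√0.85 = 0.92 at r = 0.7. Both are below 1, so power would fall.
- A reader might infer a larger bias by assuming that exactly the worst 20% of 6-month responders leave. That gives 0.35 × r, or 0.175 SD at r = 0.5 and 0.245 SD at r = 0.7. Nothing in the documents suggests that patients leave according to their own cytokine changes, and the softer simulated mechanism gives 0.767 − 0.667 = 0.10 SD.

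**Conclusion.** The concern holds in a limited form. The plan's only formal test of blood markers runs to an undefined visit, and no rule covers patients who stop after 6 months. One reading excludes them; the other mixes treatment durations.

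The size cannot be derived from the documents. Under the assumed 20% response-related dropout and a true change of 0.667 SD, the error is about 15% upward for completers or 17% downward for last attended visit. The likelihood-based estimate is unbiased when dropout depends on the observed 6-month value; dropout driven by unobserved values would still bias it. The precision gain is small: effective n about 20 to 22 against about 19 completers, for r between 0.5 and 0.8, and less in practice at the low end. If nobody drops out, the estimated 1-year change is the same.

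These are additional outcomes and the primary result is not affected. The change is worth making because it is cheap and removes a choice that could otherwise follow the data.

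**What to change.** In Statistical Procedures, replace the undefined visit with the 1-year visit. For each marker, fit one likelihood-based mixed model for repeated measures with baseline, 6 months and 1 year as categorical visits, keeping every available value from patients who stop early. An unstructured within-patient covariance (six parameters for three visits) with a small-sample degrees-of-freedom correction is suitable. Use the log scale for skewed markers, as the plan already allows. For fasting glucose, state which of its six visits enter the model.

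Report the baseline-to-1-year contrast with its confidence interval as the single main result for each marker, so that the planned multiplicity correction does not have to cover more tests. Label any average on-treatment contrast as supportive, because it answers a different question. Report how many patients contribute at each visit, and state the missing-at-random assumption.

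The cost is a few sentences in the SAP and slightly more analysis work in standard software. No new samples or visits are needed. The price is reliance on the missing-at-random assumption, which the data cannot confirm.
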